4.1 Objectives

To assess the feasibility of conducting a randomised controlled trial (f-RCT) of a BRIDGE, a brief intervention programme for young people (age 14-24) with early BPD (sub-threshold or threshold) in the general population of Glasgow, Scotland.

4.2 Primary outcome measures

1. Are young people early in the course of BPD willing to be randomised to BRIDGE (AND service as usual) or service as usual (ALONE).
2. Can sufficient numbers of young people be recruited and retained such that a full-scale RCT is likely to be feasible in the future?

4.3 Secondary outcome measures

1. How acceptable are the trial processes and interventions to the participants?
2. Can data systems be set up for assessment of both clinical and health economic outcomes in a future definitive randomised controlled trial (d-RCT)?
3. Does the trial need adapting for participants in different settings (process evaluation and qualitative interviews)?

The putative outcome measures for baseline and follow-up assessments have been selected after consulting the Delphi report from International Committee for Harmonization of Outcome Measures for Personality Disorder (http://www.netscc.ac.uk/hsdr/files/project/SDO_FR_08-1404-083_V0.1.pdf).

The f-RCT will investigate the acceptability and appropriateness of these measures for a future d-RCT which include, at screening/pre-randomisation: SCID-II PQ-BPD; SCID-II DSM-V (BPD module); KIDSCREEN10; Pathways to Care and Demographics. Post randomisation: Mini International Neuropsychiatric Interview (MINI) 7.0.2 (18yrs+) and the Mini International Neuropsychiatric Interview (MINI-KID) 7.0.2 (under 18yrs); Adverse Childhood Experiences Scale; Autism Symptoms adolescents (ASSERT); Adult ADHD Self-Report Scale (ASRS). Baseline and follow-up: Borderline symptoms list (BSL-23); Sheehan's Disability Scale (SDS); Difficulties in

Emotional Regulation Scale-SF; Patient Health Questionnaire-9; Quality of Life Questionnaire (EQ-5D); ICECAP-A; Suicidal Ideation Scale; Vocational and Educational functioning.

5 Trial design

5.1 Design

This proposed feasibility randomised controlled trial (RCT) will follow the Medical Research Council Complex Interventions Framework (Figure 1). We will randomise young people with symptoms of early BPD to BRIDGE (AND service as usual) or service as usual (ALONE) and explore aspects of feasibility using qualitative and quantitative methods. This will allow us to assess the feasibility of recruitment and retention of a sufficiently representative sample for a substantive RCT and help us determine the likely size of such a future definitive RCT.

5.1.1 Participant recruitment

Sixty young people (age 14-24) from Glasgow, experiencing symptoms of early BPD, will be recruited. Participants will be recruited through the following channels (approval dependent);

- Referral from professional within the NHS GG&C (CAMHS, AMHS, GP, A&E)
- Referral from professional within GCC education, social work, forensic services
- Referral from third sector organisations
- Self-referral through advertisements in public places (i.e. transport, libraries, social media)
- Self-referral through re-engagement letter (see Appendix 1). This method of recruitment will aim to recruit participants that have disengaged subsequent to meeting the criteria for the study where consent has been given to be contacted.

Professionals within each of the above services will be made aware of the study through conversations with the trial team. They will then be regularly asked if any patients on their caseload/service users meet inclusion criteria for the study, and can be approached for participation. With potential participants consent professionals will also have the opportunity to discuss potential referrals with the team.

The screening would include a two phased approach:

Screening Phase 1: Participants (accessed through a range of settings in Glasgow) will self-complete the brief (15-item) SCID-II PQ-BPD questionnaire. Potential participants can be either referred by a professional in a range of settings in Glasgow or can self-refer: everyone will complete either an online or paper screening assessment. Those meeting the cut off for the

SCID-II PQ BPD (>11 out of 15) will be invited to Phase 2. SCID-II PQ-BPD has excellent psychometric properties and is used as a screening tool for BPD in outpatient youth.

At Screening Phase 2, all potentially eligible participants will be invited for a short (< 10 minutes) interview conducted using the Structured Clinical Interview for DSM-V Axis II Personality Disorders (SCID-II) BPD module. The eligibility criteria for the study will be those who meet sub-threshold (3 or 4 out of 9 domains) or threshold (5 and above out of 9 domains) criteria on the SCID-II DSM-V, for intake to the BRIDGE study before randomisation.

5.1.2 Intervention

Brief, intensive assessment and integrated formulation (BRIDGE) intervention development has been guided by a) the emerging evidence base for Cognitive Analytic Therapy (CAT) with young people (age 15-25) with BPD in an early intervention service and b) in collaboration with an established Glasgow intervention programme, called Intensive Support and Monitoring Service (ISMS), used in the Glasgow youth justice system. ISMS has the explicit focus of reaching a shared formulation with the young person and the multi-agency system that supports them.

BRIDGE is delivered over 3-6 months and has a three-fold focus:

Firstly, an intensive (post-randomisation) assessment, taking up to two sessions, including BPD symptoms, copresenting difficulties, neurodevelopmental profile, life events history and psychosocial functional impact.

Secondly, up to 16 sessions of Cognitive Analytic Therapy (CAT).

Thirdly, development of a shared formulation with a multi-agency group; further development of the shared formulation with the young person, using CAT principles (Reformulation, Recognition and Revision) and, where clinically applicable, their family and service-providers.

5.1.3 Comparison

For participants randomised to Service-As-Usual (SAU), a routine letter of their participation will be shared with their service provider(s), including the GP. SAU, likely to range from social services, mental-health services, forensic services to no intervention will be mapped and described for each participant. Treatment fidelity to SAU will therefore not be assessed, but the nature and intensity of SAU in different contexts will be described in detail through the qualitative process evaluation.

5.2 Procedure

Our three-month pre-trial set-up phase will establish a detailed system for managing referrals and randomisation and network between the various services from whom we would receive referrals (see section 5.1.1), including any self-referrals/completed online questionnaires. All potential participants will receive a 'Participant Information Leaflet' and a 'Trial Consent Form' prior to Screening 1.

On completion of the Participant Information sheet (online or paper format) and consent form from young people (age 14-24), and from parents and assent from children (age 14-16 who are judged by a healthcare professional as incapable of providing consent), the trial research team (trial manager and research associate) will ensure eligible adolescents and young people are invited to screening 2 with a clinician, prior to study randomisation. Capacity to consent will be confirmed and documented by a healthcare professional at screening 2, prior to randomisation.

Randomisation will be controlled by the Trial Team at the University of Glasgow, who will randomise patients (1:1) to BRIDGE (+SAU) or SAU. The trial manager will generate a randomisation list to ensure data collector blindness. The randomisation list containing the unique study ID and participant name will be stored in a password protected file within the Trial Team's private Microsoft Teams channel (following GDPR guidelines at the university of Glasgow secure server), and access will be restricted only to those members of the research team who will remain unblinded throughout the study. A log of access will be maintained.

All participants consenting to participate will be invited to complete assessments, post randomisation, at baseline, 12 and 24 weeks follow up. A minimum data set of care pathways will be described at baseline and follow-up for all participants, for the purposes of future modelling of health economics impacts, in relation to putative quality of life and functional outcomes measures. Case-study methodology will be used to understand individual contexts, involving qualitative interviews with fourteen young people (seven from BRIDGE intervention and seven from SAU's) and, where possible, their parents and relevant service providers. Topics will include acceptability of the three elements of BRIDGE, perceived mechanisms of change and exploration of requirements for data collection for a future d-RCT, including for future health economic evaluation.

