Rationale	Young people with early BPD benefit from good clinical care and targeted intervention, however are regularly missed or mis-labelled. The feasibility trial in the general population would provide initial evidence of variable needs of young people with complex needs, who maybe missed from services as they don't "fit" a model/diagnosis. Workable multi-agency service model proposed in the trial would be a major advance in understanding care pathways regardless of trial outcome.
Methodology	We plan to conduct an f-RCT following the Medical Research Council Complex Interventions Framework.
Sample size	Our pilot work suggests that the sample size (N=60) and timescale for recruitment and randomisation, intervention delivery and for follow-up data collection is appropriately estimated. The sample of the feasibility study is adequate to estimate clinical parameters of recruitment and retention. We will

[figure not shown]
	
use the standard deviations of the putative outcome measures used in this study for the power calculations for the definitive RCT.

Screening	
The screening would include a two phased approach:
 
Screening Phase 1 : Participants (accessed through a range of clinical and non-clinical settings in Glasgow) will self-complete the brief (15-item) SCID-II PQ-BPD questionnaire. Potential participants can be either referred by a professional in a range of services in Glasgow (e.g. health, social, education) or can self-refer through advertisements in public places: everyone will complete either an online or paper screening assessment. Those meeting the cut off for the SCID-II PQ BPD (>11 out of 15) will be invited to Phase 2. SCID-II PQ-BPD has excellent psychometric properties and is used as a screening tool for BPD in outpatient youth.
 
At Screening Phase 2, all potentially eligible participants will be invited for a short (< 30 minutes) interview conducted using the Structured Clinical Interview for DSM-V Axis II Personality Disorders (SCID-II) BPD module. The eligibility criteria for the study will be those who meet subthreshold (3 or 4 out of 9 domains) or threshold (5 and above out of 9 domains) criteria on the SCID-II DSM-V, for intake to the BRIDGE study before randomisation.

Randomisation	On completion of the baseline data collection, consenting participants will be individually randomised 1:1 to BRIDGE plus service-as-usual (SAU) or SAU.

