5.3 Measures

The putative outcome measures for baseline and follow-up assessments have been selected after consulting the Delphi report from International Committee for Harmonization of Outcome Measures for Personality Disorder (http://www.netscc.ac.uk/hsdr/files/project/SDO_FR_08-1404-083_V0_1.pdf). The f-RCT will investigate the acceptability and appropriateness of these measures for a future d-RCT which include, at screening/pre-randomisation: SCID-II PQ-BPD;

SCID-II DSM-V (BPD module); KIDSCREEN10; Pathways to Care and Demographics. Post randomisation: Mini International Neuropsychiatric Interview (MINI) 7.0.2 (18yrs+) and the Mini International Neuropsychiatric Interview (MINI-KID) 7.0.2 (under 18yrs); Adverse Childhood Experiences Scale; Autism Symptoms adolescents (ASSERT); Adult ADHD Self-Report Scale (ASRS). Baseline and follow-up: Borderline symptoms list (BSL-23); Sheehan's Disability Scale (SDS); Difficulties in Emotional Regulation Scale-SF; Patient Health Questionnaire-9; Quality of Life Questionnaire (EQ-5D); ICECAP-A; Suicidal Ideation Scale; Vocational and Educational functioning.

All the measures will be incorporated into a user-friendly questionnaire “book” and participants will have the option of completing on paper, in a telephone interview, or a mixture – a technique that has worked well in previous studies. These measures will be conducted, blind to group status, before and 12 and 24 weeks post randomization.

Analyses carried out in the f-RCT will remain blinded. Recruitment, retention rates and the BRIDGE sessions attended will be calculated with 95% confidence intervals (CI). A simple descriptive analysis of recruitment / retention relative to eligible / approached population will be conducted. While underpowered, between-group change in each measure after adjustment for baseline will be estimated using analysis of covariance (ANCOVA).

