7.2 Data Collection forms

A user-friendly booklet will be developed by the trial team incorporating relevant demographic and health economic information, as well as the following psychometrics:

Table 1. Baseline and follow-up assessments for the feasibility trial (The BRIDGE project)

Measure*	Baseline	12 wks	24 wks	What measuring?
Questionnaires				
SCID-II PQ-BPD	✓	✓	✓	BPD symptoms (self-reported)
SCID-II DSM-V (BPD module)	✓	✓	✓	BPD criteria (>3 or above out of 9 domains)
KIDSCREEN10	✓	✓	✓	Overall Functioning
Care pathways record and minimum data set	✓			Demographics, pathways to care
Questionnaires				Intensive assessment (BRIDGE)
K-SADS/PL	✓			Assessment of lifetime and present psychopathology
Adverse Childhood Experiences Scale	✓			Adverse childhood experiences
Autism Symptoms adolescents (ASSERT)	✓			Autism assessment
Adult ADHD Self-Report Scale (ASRS)	✓			ADHD symptom checklist
Putative outcome measures of change				Possible mechanisms of change
Borderline symptoms list (BSL-23)	✓	✓	✓	BPD symptom severity
Sheehan's Disability Scale (SDS)	✓	✓	✓	Functioning: work/school, social and family life
Difficulties in Emotional Regulation Scale-SF	✓	✓	✓	Domains of emotional regulation
Patient Health Questionnaire-9	✓	✓	✓	Severity of depression
Quality of life Questionnaire (EQ-5D)	✓	✓	✓	General health related quality of life

ICECAP-A	✓	✓	✓	Wellbeing assessment (Economic Evaluation)
Suicidal Ideation Scale	✓	✓	✓	Suicidal thinking and behaviours (ideation, self-harm, attempts)
Vocational and Educational functioning	✓	✓	✓	School and work (Paid and Unpaid) engagement

* The outcome measures for baseline and follow-up assessments have been selected after consulting the Delphi report from International Committee for Harmonization of Outcome Measures for Personality Disorder (http://www.netscc.ac.uk/hsdr/files/project/SDO_FR_08-1404-083_V01.pdf)

8 Randomisation

Randomisation will be controlled by the Trial Team at the University of Glasgow, who will randomise participants (1:1) to BRIDGE (+SAU) or SAU (see section 10). The trial manager will generate a randomisation list to ensure data collector blindness. The randomisation list will be stored in a password protected file within the Trial Team's private Microsoft Teams channel, and access will be restricted only to those members of the research team who will remain unblinded throughout the study. A log of access will be maintained.

9 Withdrawal & loss to follow-up

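### Section 5.2 places the baseline assessment after randomisation, against the synopsis and section 5.3; section 5.3 and Table 1 are themselves mixed, and all three need one consistent order

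*Combined protocol and SAP*

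**What the plan says.** Three statements fix the order of baseline and randomisation.

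- Section 5.2 (Procedure): "All participants consenting to participate will be invited to complete assessments, post randomisation, at baseline, 12 and 24 weeks follow up".
- Section 1 (Synopsis, Randomisation row): "On completion of the baseline data collection, consenting participants will be individually randomised".
- Section 5.3 (Measures), directly after saying that all measures go into one booklet: "These measures will be conducted, blind to group status, before and 12 and 24 weeks post randomization".

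Sections 4.3 and 5.3 also sort the instruments by timing. One group is taken "at screening/pre-randomisation: SCID-II PQ-BPD; SCID-II DSM-V (BPD module); KIDSCREEN10; Pathways to Care and Demographics". A second group opens with "Post randomisation: Mini International Neuropsychiatric Interview (MINI) 7.0.2 (18yrs" and continues with MINI-KID, the Adverse Childhood Experiences Scale, ASSERT and ASRS. A third group, labelled baseline and follow-up, holds the eight putative outcome measures: BSL-23, SDS, DERS-SF, PHQ-9, EQ-5D, ICECAP-A, the Suicidal Ideation Scale, and vocational and educational functioning.

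Table 1 (section 7.2) has a single Baseline column. It ticks the eight outcome measures there, and also the Adverse Childhood Experiences Scale, ASSERT and ASRS, in a block headed "Intensive assessment (BRIDGE".

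On blinding, sections 5.2 and 8 say "The trial manager will generate a randomisation list to ensure data collector blindness". On completion of the booklet, section 5.3 says "participants will have the option of completing on paper, in a telephone interview, or a mixture". Sections 5.3 and 13.2 plan an ANCOVA of each measure adjusted for its baseline.

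**The concern.** The Procedure section is the text that staff are most likely to work from, and it puts baseline on the wrong side of randomisation relative to two other explicit statements.

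The order matters because baseline is the ANCOVA covariate. A covariate measured before allocation cannot be affected by it. One measured after participants know their arm can be: someone told that they will not receive up to 16 sessions of therapy may score the same week differently from someone told that they will. The blinding described is that of data collectors. It does not stop the participant's own answers from moving, whether given on paper or to a blinded telephone interviewer. Adjusting for a shifted baseline then moves the between-group estimate even when there is no treatment effect.

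**Working it through.** **Step 1. The statements side by side**

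| Place | Baseline relative to randomisation |
|---|---|
| Synopsis, Randomisation | Before |
| Section 5.2 | After, on its plain reading |
| Section 5.3, sentence on conduct of the measures | Before, for all the measures |
| Sections 4.3 and 5.3, lists of instruments | MINI/MINI-KID, Adverse Childhood Experiences Scale, ASSERT and ASRS after; outcome measures labelled only baseline and follow-up |
| Table 1 | Not stated; one Baseline column holds both the outcome measures and three of the post-randomisation instruments |

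Section 5.2 conflicts with the synopsis and with the section 5.3 sentence. That sentence in turn conflicts with section 5.3's own post-randomisation list. Table 1 cannot decide between them. The participant flow diagram (section 2.1) is not shown in the text available and could not be checked.

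**Step 2. Size, if section 5.2 were followed and allocation were known**

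The plan has no figure to reproduce: N = 60 is stated without a formal calculation. From the documents come 60 participants and 1:1 allocation, hence 30 per arm. Everything else is assumed:

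- d = 0.1 to 0.3 SD, an upward shift in service-as-usual baseline scores caused by knowing the allocation
- r = 0.5 to 0.7, the baseline-to-follow-up correlation, with equal variances so that the ANCOVA slope is r
- p = 0 to 1, the fraction of the shift still present at follow-up
- no true treatment effect

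The expected ANCOVA estimate (BRIDGE minus service as usual) is the follow-up difference minus r times the baseline difference:

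- baseline before randomisation: (0 − p·d) − r·0 = −p·d
- baseline after allocation is known: (0 − p·d) − r·(0 − d) = (r − p)·d
- difference, which is the part due to baseline timing: (r − p)·d − (−p·d) = r·d

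Smallest: 0.5 × 0.1 = +0.05 SD. Largest: 0.7 × 0.3 = +0.21 SD. The term −p·d arises whenever baseline is taken, so timing does not cause it.

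**Step 3. Against the precision of the estimate**

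SE = √[(2/n)(1 − r²)], in SD units, n = 30 per arm:

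- r = 0.5: √(0.0667 × 0.75) = 0.224
- r = 0.7: √(0.0667 × 0.51) = 0.184

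With 24 per arm (80% followed, assumed), the SEs are 0.250 and 0.206. At r = 0.7 and d = 0.3 the timing bias is therefore slightly larger than one SE (0.21 against 0.184). At d = 0.1 it is 0.05 to 0.07, well under half an SE.

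**Step 4. What passes to the definitive trial**

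Section 6.3 carries forward standard deviations. A constant shift leaves the within-arm SD unchanged. A baseline SD pooled over both arms is multiplied by √(1 + d²/4), which is 1.001 at d = 0.1 and 1.011 at d = 0.3, so it rises by at most 1.1%.

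**The case against.** **It may be loose wording.** The phrase in section 5.2 may have been meant for the two follow-ups only, or to cover the intensive assessment, which really is planned after randomisation (sections 5.1.2 and 10). Either is possible, but the sentence does not say so. Because section 5.3 and Table 1 are mixed, a reader cannot resolve it from them. This objection stands in one respect: correcting section 5.2 alone would not be enough.

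**Harm needs several steps.** Section 5.2 would have to be followed, participants would have to learn their arm before completing baseline, and their answers would have to shift. The documents establish none of these, and they do not say when allocation is disclosed. This stands. A reader might infer that baseline scores were in fact collected with knowledge of allocation and that the ANCOVA is compromised; the text supports only a conflict in wording and a conditional risk.

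**A persisting shift is not a timing fault.** A reader might also take the whole quantity (r − p)·d, including its negative values, as the damage done by section 5.2. That is wrong. A shift that lasts to follow-up biases the comparison by −p·d even with a correct baseline. With r = 0.5, p = 0.5 and d = 0.3, the total is −0.15 SD with baseline before and 0 with baseline after. The timing part is +0.15 SD, and the zero is an accidental cancellation. For p above r/2 a late baseline gives the smaller total in absolute terms. That is no reason to prefer it, since the cancellation depends on quantities that nobody knows.

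**The practical stakes are low.** The primary outcomes are recruitment and retention, and the ANCOVA is declared underpowered. This stands and sets the grade.

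**Conclusion.** The contradiction holds, with high confidence as a matter of wording. The consequence is conditional and minor. Under the assumptions stated, the timing component is +0.05 to +0.21 SD, against an SE of about 0.18 to 0.22 SD with 30 per arm. Its positive sign follows from assuming that service-as-usual scores move upward; a downward move would reverse it.

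A reader might infer that the feasibility conclusions are at risk. They are not: recruitment and retention rates are counts that do not use the questionnaire scores, and the standard deviations barely change. What is exposed is the set of exploratory between-group estimates for the eight putative outcome measures. The missing flow diagram may show the intended order, but it would not remove the need to correct the text.

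**What to change.** 1. **Section 5.2.** State that the eight putative outcome measures (BSL-23, SDS, DERS-SF, PHQ-9, EQ-5D, ICECAP-A, Suicidal Ideation Scale, vocational and educational functioning) are completed before randomisation, that allocation is released only after completion is logged, and that follow-up assessments are at 12 and 24 weeks.
2. **Section 5.3.** Limit the sentence on when the measures are conducted to those eight outcome measures, so that it no longer conflicts with the post-randomisation list in the same section.
3. **Table 1.** Split the Baseline column into pre-randomisation baseline and post-randomisation intensive assessment.
4. **Participants already randomised.** Compare the baseline and randomisation dates and report how many baselines came later.
5. **If any did.** Add a sensitivity analysis without the post-randomisation covariate, or with KIDSCREEN10, which sections 4.3 and 5.3 label pre-randomisation. State that it removes only the timing component r·d and leaves any persisting shift −p·d.

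**Cost.** The text changes are an amendment for the Study Steering Committee to agree (section 17.2). No visit is added, because the synopsis and section 5.3 already ask for baseline first. The check needs two dates for at most 60 people. The sensitivity analysis loses precision: with 30 per arm the SE is √(2/30) = 0.258 SD with no covariate. With KIDSCREEN10 it is √[(2/30)(1 − 0.3²)] = 0.246 to √[(2/30)(1 − 0.5²)] = 0.224 SD, at an assumed correlation of 0.3 to 0.5 with the outcome. That is about 0.22 to 0.26 SD, against 0.18 to 0.22 SD for the planned ANCOVA.
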